### 3.4 Outcome Measures and Follow-up Plan

Primary outcome measure: Incidence of PONV within 48 hours postoperatively. PONV will be assessed within 48 hours postoperatively in the ward by a blinded investigator. Subjects are required to use the simplified PONV impact scale to report whether any PONV events occurred in the past 48 hours and to provide a rating.

(Consisting of two questions: Q1. Have you experienced vomiting or symptoms of vomiting? If yes, how many episodes in total? Under what circumstances did it occur? Was any medication administered for treatment? Q2. Have you experienced nausea? If yes, did the sensation of nausea affect your daily activities? Was any medication administered for treatment?) Based on the number, frequency, and triggers of nausea and vomiting, the incidents are classified into four grades: absence of vomiting or nausea not requiring rescue treatment after onset is defined as complete remission; Mild PONV is defined as mild nausea or a single episode of vomiting

induced by drinking water or physical activity. Moderate PONV is defined as two episodes of vomiting or significant nausea requiring rescue therapy. Severe PONV is defined as more than two episodes of vomiting or the need for more than one dose of rescue therapy.

General patient data: including age, height, weight, BMI, ASA classification, smoking history, previous history of PONV, history of motion sickness, surgical history, history of hypertension, history of diabetes, among others.

Intraoperative indicators: surgical method, surgical site, blood loss, operative duration, anesthesia duration, anesthetic dosage, infusion volume, and incidence of hypotension.

Secondary outcome measures:

1) Record the occurrence of PONV separately for four time periods (T1: PACU stay; T2: from departure from PACU to 12 hours postoperatively; T3: 12 to 24 hours postoperatively; T4: 24 to 48 hours postoperatively). Incidence of postoperative vomiting (POV) and POV scores during the four time periods (T1–T4) within 48 hours after surgery. Record the use of rescue antiemetic medications.

Postoperative analgesia assessment: Resting visual analog scale (VAS) pain scores at four time points (T1–T4) within 48 hours after surgery, measured using a 10 cm movable ruler with a numerical scale of 0–10 on the reverse side. The left end (“0”) indicates no pain, while the right end (“10”) represents unbearable severe pain. Record the number of PCA presses, total analgesic consumption, and the use of rescue analgesics within 48 hours after surgery.

Ramsay sedation score at 2 hours postoperatively: a score of 1 indicates agitation, 3 or 4 indicates somnolence, and 5 or 6 indicates excessive sedation.

Sleep quality score on the night after surgery: Patient sleep quality will be assessed using a numerical rating scale based on an 11-point Likert scale, ranging from 0 to 10. A score of 0 indicates complete insomnia and extremely poor sleep quality, while a score of 10 represents excellent sleep quality. Severe insomnia is defined as a score of 0–3, moderate insomnia as 4–6, and good sleep quality as 7–10.

QOR-15 score: A score of 0 indicates extremely poor quality of recovery, while a score of 150 indicates excellent quality of recovery. Assessments will be conducted preoperatively, on postoperative day 1, and on postoperative day 3.

Length of stay in the recovery room, time to first postoperative bowel movement, time to resumption of oral intake, time to first postoperative feeding, time to first

postoperative ambulation, and any other adverse events.

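### The four PONV grades in section 3.4 overlap and leave a gap, and no sentence says whether the grades or the yes/no answers decide the primary event

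*Combined protocol and SAP*

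**What the plan says.** Section 3.4 (Outcome Measures and Follow-up Plan) of the combined protocol and SAP sets the endpoint as "Primary outcome measure: Incidence of PONV within 48 hours postoperatively". Patients use a simplified impact scale to "report whether any PONV events occurred in the past 48 hours" and also to give a rating. The scale has two opening yes/no items: "Have you experienced vomiting or symptoms of vomiting" (item Q1) and "Have you experienced nausea" (item Q2). Follow-up questions cover the number of episodes, the circumstances, the effect on activities and any medication.

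The section then says that "the incidents are classified into four grades". The first two are introduced as "absence of vomiting or nausea not requiring rescue treatment after onset is defined as complete remission; Mild PONV is defined as mild nausea". The Mild grade also takes in one vomiting episode, with the condition "induced by drinking water or physical activity". Next comes "Moderate PONV is defined as two episodes of vomiting or significant nausea requiring rescue therapy". Severe PONV needs more than two episodes or more than one rescue dose.

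Section 3.3 makes antiemetic rescue depend on PONV reaching grade 2, but the grades in 3.4 carry no numbers. Section 3.5 bases the sample size on the 48-hour incidence. It gives general tests for categorical and ordinal data and does not say which answers or grades make a patient an event.

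**The concern.** A grading scale should put every patient in one category and only one. Here one common kind of patient appears to qualify for two categories, one of which sounds like a treatment success and the other like a PONV event. Another kind of patient qualifies for none.

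This would matter little if the plan said that the primary event is decided without the grades. It does not say so. The only definitions of PONV categories in the document are these grades, and the first carries a name that invites scoring as no event. Section 1 makes that more than a remote possibility: it describes an earlier exploratory analysis whose composite success was no vomiting and no rescue antiemetic, under which nausea without rescue counts as success. What is at stake is the numerator of the primary comparison, and the freedom to choose between two event definitions after the data are seen.

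**Working it through.** No arithmetic applies. The check sets the definitions side by side and runs two patients through them.

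**Patient A: mild nausea, no vomiting, rescue not required.** The result depends on how the first definition is parsed.

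| Reading of complete remission | Complete remission? | Mild PONV? |
|---|---|---|
| No vomiting, and any nausea needed no rescue (more natural) | Yes | Yes |
| Strict either/or: no vomiting, or nausea that needed no rescue | Yes | Yes |
| Neither vomiting nor nausea | No | Yes |

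Mild PONV applies throughout because mild nausea carries no rescue condition. Only the third reading removes the overlap. It leaves the phrase about rescue after onset with nothing to do, since a patient without symptoms has no onset. If the trigger condition in the Mild grade is read as limiting nausea too, the overlap remains, on the first two readings, for mild nausea that was so triggered.

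**Patient B: one vomit, not triggered by drinking or activity, no nausea, at most one rescue dose.**

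- Complete remission: no, on all three readings. The patient vomited and had no nausea.
- Mild: no. There was no nausea, and the vomit lacks the required trigger.
- Moderate: no. There was one episode rather than two, and no nausea.
- Severe: no. There were not more than two episodes and not more than one rescue dose.

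Patient B fits no grade, whichever parse is used.

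**Effect on the primary outcome.** Score both patients under the two rules that the text leaves open.

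| Rule for an event | Patient A | Patient B |
|---|---|---|
| Any yes to scale item Q1 or Q2 | Event (item Q2) | Event (item Q1) |
| By grade, complete remission scored as no event | No event or event, depending on which of two grades is assigned | Undefined |

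The same records can therefore give different incidences.

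**Numbering.** If complete remission is the first of the four grades, grade 2 is Mild. If counting starts at Mild, grade 2 is Moderate. Section 3.4 does not settle which, so sections 3.3 and 3.4 do not connect.

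**The case against.** The strongest reply is that the primary outcome is already clear. Patients report whether any event occurred and, separately, give a rating. The grades then sort incidents that have already been identified, and the endpoint is called an incidence in both 3.4 and 3.5, never a grade. On this view the faults touch the severity rating only. Much of this stands: the wording does lean towards any nausea or vomiting. But the sentence describes how the scale is used. It does not say that a yes is the primary event, and nothing bars complete remission from being scored as no event.

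A worst-grade rule might be assumed. None is written, and it would leave Patient B ungraded.

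A reader might also infer stronger points that the documents do not support:

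- *Significant nausea without rescue always falls outside the PONV grades.* The text turns on whether rescue was required, not whether it was given. Significant nausea that required rescue but did not receive it is Moderate as written. If rescue was not required, the more natural reading places a patient without vomiting in complete remission, which is itself one of the four grades.
- *The number of overlapping or ungraded symptom patterns measures the problem.* Any such tally changes with the parse and counts patterns, not patients.
- *The trial is underpowered, or its sample size is wrong.* The documents give no share of nausea that needs no rescue, so no loss can be derived.
- *A planned ordinal analysis of the grades fails.* The rank-sum sentence in 3.5 is general. The secondary outcomes list PONV occurrence by period, vomiting incidence and vomiting scores. No passage names the four-grade rating as an analysed outcome.

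**Conclusion.** The point holds as a conflict within the stated classification, plus a missing event rule. Three things stand: Patient A's double classification on the more natural reading, Patient B's lack of any grade on every reading, and the unnumbered grades behind the reference to grade 2 in section 3.3. The first depends on parsing; the other two do not.

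The link to the primary outcome is conditional. If any yes to either item is the event, the faults stay within the severity rating. If the grades decide, they reach the primary incidence. The documents favour the first without stating it. No effect size is claimed. This should be fixed before unblinding, because the choice of rule would otherwise remain open once results are known.

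**What to change.** In section 3.4, before unblinding:

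1. State that the primary event is any yes to scale item Q1 or Q2 within 48 hours, regardless of severity or rescue, and that the grades describe severity only.
2. Redefine the top category as no nausea and no vomiting, that is, no to both items.
3. Reword the remaining grades so that each patient with an event falls in exactly one, including a patient with a single unprovoked vomit.

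The investigators must also reconcile the grade reference in section 3.3 with the unnumbered grades in 3.4. No rescue threshold is proposed here.

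The cost is protocol and case report form wording. The answers to both items, the circumstances of vomiting and the use of rescue antiemetics are already collected, so no extra patients or visits are needed.

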### 3.5 Statistical Analysis Plan

Sample size calculation: The primary outcome is the incidence of PONV within 48 hours postoperatively, and the sample size will be calculated based on this primary endpoint. According to the study by Zhao et al., the incidence of PONV within 48 hours after gynecological laparoscopic surgery is 71.7%. It is expected that the incidence of PONV will be reduced by at least 40%. Assuming  $\alpha = 0.05$  and a power of 80%, PASS 15 software was used to calculate a sample size of  $N = 45$  per group. Considering a 5% dropout rate, a total of 48 patients per group will be enrolled, requiring 96 subjects in total.

Statistical analysis was conducted using SPSS 26.0. Normally distributed continuous data were expressed as mean  $\pm$  standard deviation (mean  $\pm$  SD), and between-group comparisons were performed using the independent samples t-test. Non-normally distributed continuous data were expressed as median (M) and interquartile range (IQR), and between-group comparisons were performed using the Wilcoxon rank-sum test. Repeated measures data were analyzed using repeated measures analysis of variance or the generalized estimating equation model, according to the distribution characteristics of the data. Categorical data were expressed as rates or percentages, and comparisons were performed using the  $\chi^2$  test or Fisher's exact test. Ordinal data were analyzed using the rank-sum test. Subgroup analyses will be performed based on operative duration ( $\leq 2$ h or  $> 2$ h), smoking status (non-smoker or history of smoking within the past six months), history of chemotherapy, age ( $\leq 50$  or  $> 50$ ), and BMI (18-25 or 25-30), using logistic regression analysis. A P value  $< 0.05$  will be considered statistically significant.

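### Time to first bowel movement and the other recovery times have no end of observation and no rule for a patient without the event

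*Combined protocol and SAP*

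**What the plan says.** The combined protocol and SAP, section 3.4 (Outcome Measures and Follow-up Plan), closes its secondary outcomes with a list of recovery times: "time to first postoperative bowel movement, time to resumption of oral intake, time to first postoperative feeding", followed by first ambulation. No assessment occasion, source of the data, end of observation or handling of a patient without the event is attached to them.

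Most other items in that section are dated. For the primary outcome, "PONV will be assessed within 48 hours postoperatively in the ward by a blinded investigator". VAS pain, PCA presses, analgesic consumption and rescue analgesics also run to 48 hours. Sedation is scored at 2 hours and sleep on the night after surgery. For the QoR-15, "Assessments will be conducted preoperatively, on postoperative day 1, and on postoperative day 3". That day-3 assessment is the latest contact scheduled anywhere in the plan.

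Section 3.5 (Statistical Analysis Plan) sorts continuous data by distribution. For normal data, "between-group comparisons were performed using the independent samples t-test". Otherwise, "Non-normally distributed continuous data were expressed as median (M) and interquartile range (IQR), and between-group comparisons were performed using the Wilcoxon rank-sum test". No Kaplan–Meier, log-rank or Cox method appears, and there is no censoring or missing-data rule.

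**The concern.** A time to event is known only for patients who have had the event while someone was recording it. A patient on opioid analgesia with no bowel movement at the last contact has no completed time. Neither listed test can use a blank, and the plan does not say what to enter instead.

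If such patients are left out, the loss is not random: they are the slowest patients, and there are more of them in the slower arm. Both arms then look faster than they are, the slower arm more so. What is at stake is the estimated difference, the reported medians and the power for these outcomes. Because the rule is unwritten, the choice would also be made after the data are seen.

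**Working it through.** **The plan's own figure.** The only sizing figure is for PONV. Inputs from section 3.5: control rate 0.717, a 40% reduction (read as relative, so 0.717 × 0.6 = 0.4302), α = 0.05 (two-sided assumed) and power 80%. With the pooled formula and p̄ = 0.5736:

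n = [1.96·√(2 × 0.5736 × 0.4264) + 0.8416·√(0.717 × 0.283 + 0.4302 × 0.5698)]² / 0.2868² ≈ 45.5, so 46 per group against the stated 45.

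Inflating for dropout, 45/0.95 = 47.4, so 48 per group as stated. The figure reproduces to within one patient. It does not bear on the recovery times; only the 48 per arm is carried forward.

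**Assumed inputs.** The documents give no bowel-movement times. Times are taken as lognormal with log-SD 0.5, and three pairs of medians are tried. Observation is cut at 72 h, an assumed reading of the day-3 contact.

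**Share without an event.** P(T > 72) = 1 − Φ(ln(72/median)/0.5). For a median of 36 h, ln(2)/0.5 = 1.386, giving 8%. For 48 h, ln(1.5)/0.5 = 0.811, giving 21%. The other medians follow in the same way.

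**Simulation.** There were 2,000 trials per setting with 48 per arm. The two-sided rank-sum test at 0.05 was applied to (a) complete times, (b) times with no-event patients deleted and (c) all patients, with no-event patients tied at the worst rank.

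| True medians (h) | No event by 72 h | Medians after deletion (h) | Gap: true → after deletion (h) | Power (a) complete | Power (b) deleted | Power (c) worst rank |
|---|---|---|---|---|---|---|
| 24 vs 32 | 1% vs 5% | 23.9 vs 31.2 | 8 → 7.3 | 0.79 | 0.71 | 0.79 |
| 36 vs 48 | 8% vs 21% | 34.3 vs 42.1 | 12 → 7.8 | 0.77 | 0.52 | 0.76 |
| 48 vs 60 | 21% vs 36% | 42.1 vs 47.5 | 12 → 5.4 | 0.56 | 0.23 | 0.55 |
| 30 vs 30 | 4% vs 4% | 29.4 vs 29.4 | 0 → 0 | 0.053 | 0.050 | 0.052 |

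The simulation error is about √(0.5 × 0.5/2000) = 0.011 for powers near one half and √(0.05 × 0.95/2000) = 0.005 for the last row.

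**Reading the table.** Deletion shortens both medians and narrows the gap in every setting with a true difference. The size runs from slight to large with the assumed medians. With equal arms the rejection rate stays at its nominal level. Keeping the no-event patients at the worst rank recovers almost all of the power.

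**The case against.** A reader might infer that the plan drops patients who have had no bowel movement. It does not say so. Section 3.5 mentions no exclusion, and leaving out a blank value is only the likely software default. The case report forms are separate documents (section 4) and may provide for this, and ward records could supply the times. All of that stands, so the concern is conditional. The source and the rule still need to be written down.

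A reader might also infer that observation stops at 48 hours. In the 36 vs 48 h setting that would leave 28% vs 50% without an event, with power 0.25 after deletion. But the 48-hour limit belongs to PONV, pain and analgesic use, and the QoR-15 contact comes later. The documents do not support those figures as the expected loss.

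A third tempting reading is that the rank-sum test is the wrong method. It is not: with one common cut-off and no-event patients tied at the worst rank it performs well, as the last column of the table shows. What is missing is the coding rule. The t-test is different, because it has no comparable way to use a patient without a completed time.

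Finally, the importance is limited. Section 2 names PONV as the sole objective, and the clinical evidence in section 1 concerns nausea, vomiting and rescue antiemetics. Bowel movement is one unranked item in a list for which the trial is not powered. The bias runs towards no difference, so it would not manufacture a benefit for oliceridine. This stands too, and it limits the point to a cheap improvement.

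**Conclusion.** The point holds in conditional form. The recovery times have no stated source, end of observation or no-event rule, and the listed tests cannot use a patient without a completed time. If such patients are left out, medians are too short and a true difference is understated, at the cost of power but not of type I error.

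The size cannot be derived from the documents. Under the assumptions above (lognormal times, log-SD 0.5, 72-h cut-off, 48 per arm), the loss of power ranges from 0.08 (0.79 to 0.71) to 0.33 (0.56 to 0.23). It is nil if every patient has the event by day 3. The primary PONV result is unaffected. This is a cheap improvement to secondary outcomes.

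**What to change.** - **Section 3.4:** state the data source. At the existing contacts through postoperative day 3, record the date and time of first bowel movement, oral intake, feeding and ambulation. Mark a patient who has not had the event as censored at the day-3 contact.
- **Section 3.5:** analyse these times by Kaplan–Meier with a log-rank test. Alternatively, keep the rank-sum test and give patients without the event the tied worst rank at one common cut-off, which must be a time that every patient's day-3 contact has reached. Do not use a t-test on completed times.
- **Reporting:** give the number without each event by arm. If half or more of an arm has not had the event by the end of observation, the Kaplan–Meier median may not be estimable, and this count then carries the result.

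The cost is one added question at contacts already planned and two sentences in the analysis plan. No visit is added, and the sample size does not change.

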### 3.5 Statistical Analysis Plan

Sample size calculation: The primary outcome is the incidence of PONV within 48 hours postoperatively, and the sample size will be calculated based on this primary endpoint. According to the study by Zhao et al., the incidence of PONV within 48 hours after gynecological laparoscopic surgery is 71.7%. It is expected that the incidence of PONV will be reduced by at least 40%. Assuming  $\alpha = 0.05$  and a power of 80%, PASS 15 software was used to calculate a sample size of  $N = 45$  per group. Considering a 5% dropout rate, a total of 48 patients per group will be enrolled, requiring 96 subjects in total.

Statistical analysis was conducted using SPSS 26.0. Normally distributed continuous data were expressed as mean  $\pm$  standard deviation (mean  $\pm$  SD), and between-group comparisons were performed using the independent samples t-test. Non-normally distributed continuous data were expressed as median (M) and interquartile range (IQR), and between-group comparisons were performed using the Wilcoxon rank-sum test. Repeated measures data were analyzed using repeated measures analysis of variance or the generalized estimating equation model, according to the distribution characteristics of the data. Categorical data were expressed as rates or percentages, and comparisons were performed using the  $\chi^2$  test or Fisher's exact test. Ordinal data were analyzed using the rank-sum test. Subgroup analyses will be performed based on operative duration ( $\leq 2$ h or  $> 2$ h), smoking status (non-smoker or history of smoking within the past six months), history of chemotherapy, age ( $\leq 50$  or  $> 50$ ), and BMI (18-25 or 25-30), using logistic regression analysis. A P value  $< 0.05$  will be considered statistically significant.

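### The rule choosing between repeated-measures ANOVA and GEE for the repeated secondary scores is undefined, and there is no rule for missed assessments, so a patient with one missing value can be lost

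*Combined protocol and SAP*

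**What the plan says.** Section 3.5 deals with repeated outcomes in one sentence: "Repeated measures data were analyzed using repeated measures analysis of variance or the generalized estimating equation model, according to the distribution characteristics of the data". It names no normality test, cut-off, covariance structure or target effect (arm, or arm by time), and it does not list the outcomes covered. The sentences just before it divide single-time continuous data into normal (t-test) and non-normal (rank-sum test).

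Section 3.4 supplies the repeated outcomes, all secondary:
- pain: "Resting visual analog scale (VAS) pain scores at four time points (T1–T4) within 48 hours after surgery";
- QoR-15: "Assessments will be conducted preoperatively, on postoperative day 1, and on postoperative day 3";
- PONV and vomiting in four periods, T1 to T4.

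No section defines an analysis set or says what happens to a missed assessment. The only related figure is in the sample size paragraph: "Considering a 5% dropout rate, a total of 48 patients per group will be enrolled". The software statement is "Statistical analysis was conducted using SPSS 26.0".

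**The concern.** The sentence raises two problems.

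First, classical repeated-measures ANOVA needs a complete row per patient. One missed ward assessment removes that patient's other scores as well, and nothing in the plan prevents this. GEE and mixed models keep the scores that were obtained. How a method treats incomplete, correlated data is therefore at least as important as the shape of the distribution, yet distribution is the only criterion given.

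Second, if distribution characteristics means how the scores look once collected, the model is chosen after seeing the outcome. With no stated test, either model could be defended.

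What is at stake is the reading of the main result. The trial compares two opioids, and section 1 says that conventional opioids raise PONV risk with dose. Less PONV with equal analgesia and less PONV with poorer analgesia are different findings. The pain and recovery comparisons separate them, so they should use all the data collected.

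**Working it through.** **Inputs from the documents.** 48 patients per group, 96 in total; 5% dropout allowance; alpha 0.05 (taken as two-sided, since sidedness is not stated); four VAS assessments; three QoR-15 assessments.

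**Assumptions, because the documents give no figure.** Missing rate m per assessment, independent across assessments; VAS SD 2 cm; correlation 0.5 between any two times; true arm difference 1 cm at every time.

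**The plan's own figure.** With 71.7% against 0.6 × 71.7% = 43.0%, 80% power and two-sided alpha 0.05, the pooled formula gives 46 per group and the unpooled formula 42.8. The stated 45 is consistent with these. Then 45/0.95 = 47.4, rounded up to 48. The point below uses only the 48 and the 5%.

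**Step 1: patients with complete rows.** With k assessments the complete share is (1 − m)^k.

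| m | VAS, k = 4 | of 96 | QoR-15, k = 3 | of 96 |
|---|---|---|---|---|
| 2% | 92.2% | 88.5 | 94.1% | 90.4 |
| 3% | 88.5% | 85.0 | 91.3% | 87.6 |
| 5% | 81.5% | 78.2 | 85.7% | 82.3 |
| 10% | 65.6% | 63.0 | 72.9% | 70.0 |

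If instead the 5% allowance covers every incomplete patient, 0.95 × 96 = 91.2 remain.

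**Step 2: power for the VAS arm effect.** The ANOVA arm effect is a t-test on patient means. The variance of a four-time mean is 2² × (1 + 3 × 0.5)/4 = 2.5. The standard error is √(2 × 2.5/n), with n complete patients per arm.

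| Case | n per arm | SE (cm) | Power, normal formula | Power, t |
|---|---|---|---|---|
| No missing | 48 | 0.323 | 87.2% | 86.6% |
| 5% of patients incomplete | 45.6 | 0.331 | 85.5% | 84.8% |
| m = 3% | 42.5 | 0.343 | 83.0% | 82.2% |
| m = 5% | 39.1 | 0.358 | 79.9% | 78.8% |
| m = 10% | 31.5 | 0.398 | 70.9% | 69.5% |

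For the last three rows, simulation (1,500 trials per rate) gave 82.3%, 79.7% and 69.1% for complete cases. A model using all observations gave 86.9%, 87.3% and 87.3%.

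**Step 3: bias.** Suppose low pain at T3 makes the T4 score more likely to be missing, with 11–25% of T4 scores missing. The complete-case estimate was then 0.94 for a true +1.0 and −0.91 for a true −1.0. The all-data model gave 1.01 and −1.00. The shortfall is 0.06–0.09 cm, against a standard error of about 0.32 cm.

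**Step 4: the data-driven choice.** Under no arm difference (4,000 trials per setting, 48 per arm, 0–10% missing), a mechanical normality gate rejected in 4.6–5.3% of trials for normal scores and 5.2–6.0% for scores rounded to 0–10 (assumed mean 2, SD 1.5). Taking the smaller of the two P values rejected in 6.5–7.6% with 2–10% missing.

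**Step 5: which scores reach the ANOVA.** In those simulations normal scores passed the gate in about 81–82% of trials, and the rounded 0–10 scores never did. Under a normality reading, VAS recorded in whole numbers would probably go to GEE, leaving QoR-15 as the likelier ANOVA candidate. If the rule means outcome type, both continuous scores go to ANOVA and the yes/no outcomes to GEE.

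**The case against.** The best defence is that distribution characteristics can mean type of outcome. PONV by period is yes/no, which ANOVA does not suit and GEE does; VAS and QoR-15 are continuous. That split is known in advance and is sensible. The sentence allows this reading, under which the choice of P value disappears. The loss of incomplete patients remains, because both continuous scores then go to ANOVA.

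Several stronger readings are tempting and should be resisted:
- A reader might infer that scores default to ANOVA, or that the plan discards patients. It says neither. The loss is a property of the classical method, left open by the plan's silence on missing values.
- A reader might take the 70% power figure as the expected result. It needs a third of patients to be incomplete. The plan's only figure is a 5% allowance, under which about two points of power are lost.
- A reader might infer serious bias or inflated false positives. The bias in step 3 is small beside the standard error and rests on an assumed mechanism. A mechanically applied gate adds little error; the 6.5–7.6% needs someone to choose the more favourable result.
- A reader might expect GEE to settle the matter. Standard GEE uses all available data but is valid only if values are missing completely at random.

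**Conclusion.** The point holds in a limited form. The sentence does not fix the model for any repeated secondary outcome, and the plan has no rule for missed assessments. On either reading, some continuous score can reach an ANOVA that drops every patient with one missing value. QoR-15 is the most exposed; VAS is exposed if judged normal or if the rule means outcome type.

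The size depends on missingness that the documents do not give. It runs from about two points of power, if 5% of patients are incomplete, to about 17 points (87% to 70%) at an assumed 10% missing per assessment. These figures also rest on the assumed SD, correlation and 1 cm difference, and on independent missingness.

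The primary outcome is a single 48-hour incidence and is untouched, so nothing here questions the main PONV comparison. The change is worth making because it is cheap and protects the secondary results needed to interpret that comparison.

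**What to change.** Replace the sentence with one pre-specified model per repeated outcome, using all available observations of all randomised patients:

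- **VAS at T1–T4:** linear mixed model with arm, time, arm by time and unstructured covariance.
- **QoR-15 on days 1 and 3:** the same model, adjusted for the preoperative score. State how a missing preoperative score is handled, since a missing covariate would otherwise drop the patient.
- **PONV and vomiting by period:** logistic GEE with arm by period, stating that it assumes values missing completely at random.

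Add a short missing-data sensitivity analysis. Report arm differences with 95% confidence intervals, averaged over time and at each time for the continuous scores. State that no model is chosen from the observed distribution.

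The cost is SAP wording and slightly more analysis work; the named software already offers both methods. One limitation is that the mixed model relies on approximate normality of mean differences for a bounded score.
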